**APPENDIX 2**

To classify the symptom score and viral load assessments to their appropriate visit identifier, the difference in days between the date of the assessment and the date of the first dose will be calculated, and this difference will be classified according to the reporting windows below. This algorithm will ensure that Day X for symptom score will correspond to Day X for viral load. As per the study protocol, Day 1 corresponds to the date of 1st dose in which all assessments were to be done PRIOR to first dose.

Once the visit identifiers are sorted out, Day 1 will be used to establish a baseline visit. If a subject has no Day 1 assessment but a screening one, then the screening assessment is chosen.

In cases where more than one assessment falls within the same reporting window, the first assessment will be chosen.

Note: For the symptom score, if both ePRO and eCRF assessments were done on the same day, then the ePRO was favored.

**Reporting windows for the classification of the visit identifiers for symptom score and viral load\***

VISIT**	SCHEDULED WINDOW (± DAYS)	DIFFERENCE BETWEEN DATE OF ASSESSMENT AND DATE OF 1 ST DOSE
*Screening	---	<0
*DAY 1	---	0
DAY 2	---	1
DAY 3	---	2
DAY 4	---	3
DAY 5	---	4
DAY 6	---	5
DAY 7	---	6
DAY 8	---	7
DAY 9	---	8
DAY 10	---	9
Follow-up visit 1 (DAY 14)	±2	11 to 15
Follow-up visit 2 (DAY 28/EOS)	±2	25 to 29

\*Screening and Day 1 will not be reported separately but will be used to classify the baseline visit as detailed above.

\*\*Viral loads are presented ONLY at baseline, Day 3, Day 5, Day 7, Day 10 & Day 28/EOS.

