##### **6.4.2 Key Secondary Analysis**

#### 6.4.2.1 Change from Baseline in log10 Viral Load

Log10 viral load, as assessed using the saliva and as assessed using the nasal swab, will be summarized by treatment group using descriptive statistics (N, mean, median, standard deviation, minimum, and maximum) for each visit as well as for changes from baseline where an 80% CI will also be presented.

Mean changes from baseline will be analyzed using a repeated measures ANCOVA model including effects of treatment, visit (Day 3, Day 5, Day 10 and Day 28/EOS), and treatment-by-visit interaction, as well as baseline value of log10 viral load and baseline value of log10 viral load-by-visit-interaction. An unstructured covariance structure will be used to model the within-patient errors and the Kenward-Roger approximation will be used to estimate denominator degrees of freedom. The combined two highest treatment groups will be compared to placebo in addition to the comparison of individual doses at the following study visits (Day 3, Day 5, Day 10 and Day 28/EOS).

Since oragene and nasal samples are collected by the subjects themselves (visit identifiers may be unreliable), an algorithm (presented in Appendix 2) was developed to classify the day of assessment into their respective visit identifiers. This algorithm is based on the fact that Day 1 corresponds to the date of the first dose and as such, will be used as baseline when available. This is in alignment with the study protocol that identifies Day 1 as the date of first dose. It is understood that all protocol assessments collected on Day 1 were to be done PRIOR to the first dose. Therefore, Day 1 will correspond to baseline when available. Please refer to Appendix 2 for more details.

A plot of mean change from baseline in log10 viral load with 80% CI at each study visit will also be presented (Section 7, Figure 4).

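### The one-day viral-load windows on Days 3, 5, 7 and 10 leave a sample taken a day off target without a visit in the tables and, for Days 3, 5 and 10, in the key secondary model

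*SAP*

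**What the plan says.** SAP Appendix 2 takes the days from first dose to each assessment, and "this difference will be classified according to the reporting windows below". One table serves both symptom scores and viral load. Days 1 to 10 each have a single value and no tolerance. The two follow-up visits have one: "Follow-up visit 1 (DAY 14) ±2 11 to 15" and "Follow-up visit 2 (DAY 28/EOS) ±2 25 to 29".

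The note under the table adds: "Viral loads are presented ONLY at baseline, Day 3, Day 5, Day 7, Day 10 & Day 28/EOS". When several samples share a window, the rule is: "In cases where more than one assessment falls within the same reporting window, the first assessment will be chosen". There is no rule for a sample whose label is not among the presented visits.

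SAP 6.4.2.1 gives the reason for relabelling by date: "Since oragene and nasal samples are collected by the subjects themselves (visit identifiers may be unreliable), an algorithm" was developed to classify the samples. The change-from-baseline model in that section is described as "including effects of treatment, visit (Day 3, Day 5, Day 10 and Day 28/EOS), and treatment-by-visit interaction". The section states no imputation for missing visits. SAP section 1 says that viral-load analyses will carry more weight in judging proof of concept.

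The protocol's Schedule of Assessments (Appendix 4) has symptoms recorded daily for the first 10 days, but saliva and nasal samples only at Screening/Baseline and on Days 1, 3, 5, 7, 10 and 28.

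**The concern.** The same table is applied to two very different sampling schemes. With a daily diary, a one-day window costs little, because the neighbouring days are also recorded. Viral load is sampled every two or three days up to Day 10. A swab taken a day early or late is usually the only one near that visit, and nothing is scheduled to replace it. The classification labels it Day 2, 4, 6, 8 or 9, or leaves it unlabelled on Day 11. None of these is a reported or modelled viral-load visit.

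At stake is precision in a key secondary analysis that the SAP has moved up in importance. If patients who collect off schedule differ in illness from those who do not, the missing visits may also not be random. The documents give no evidence either way on that.

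**Working it through.** **Inputs.** Windows and presented visits: SAP Appendix 2. Modelled visits: SAP 6.4.2.1. Sampling schedule: protocol Appendix 4. Arm size: 52 (SAP 2.1), so 104 against 52 for the two highest doses combined against placebo. Significance level: two-sided 0.20 (SAP 6.2).

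**Reproducing the windows.** Difference = study day − 1, plus or minus the tolerance. Days 3, 5, 7 and 10 give 2, 4, 6 and 9. Day 14 ± 2 gives 13 ± 2 = 11 to 15. Day 28 ± 2 gives 27 ± 2 = 25 to 29. All agree with the SAP table.

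**Where a sample on study Days 2 to 11 ends up.**

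| Difference | Study day | Label | Presented for viral load | In the model |
|---|---|---|---|---|
| 1 | 2 | Day 2 | no | no |
| 2 | 3 | Day 3 | yes | yes |
| 3 | 4 | Day 4 | no | no |
| 4 | 5 | Day 5 | yes | yes |
| 5 | 6 | Day 6 | no | no |
| 6 | 7 | Day 7 | yes | no |
| 7 | 8 | Day 8 | no | no |
| 8 | 9 | Day 9 | no | no |
| 9 | 10 | Day 10 | yes | yes |
| 10 | 11 | none | no | no |

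Of these 10 study days, 4 are presented, 3 enter the model and 6 do neither. Day 7 is not a model visit even for a sample taken on time, so its window matters only for summaries and plots.

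**Other viral-load analyses.** Time to viral clearance (SAP 6.4.3.1) is calculated from the date of the negative test, so the windows do not touch it. The AUC (SAP 6.4.2.2) uses the trapezoidal rule to Day 10, with the last observation carried forward when assessments stop short of Day 10. The text does not say whether it uses visit labels or sampling dates. If it uses labels, a real Day 11 sample would be ignored and an older value carried forward in its place.

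**Size.** The documents give no off-day rate p, so a range is assumed, with samples lost at random and equally in all arms. Standard error factor at one visit = 1/√(1 − p). For illustration, power is for a single-visit comparison assumed to have 80% power at two-sided 0.20 with no loss: Φ((1.2816 + 0.8416)·√(1 − p) − 1.2816).

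| p | Patients left (from 104 vs 52) | Standard error factor | Power |
|---|---|---|---|
| 5% | 98.8 vs 49.4 | 1/√0.95 = 1.026 | 78.5% |
| 10% | 93.6 vs 46.8 | 1/√0.90 = 1.054 | 76.8% |
| 20% | 83.2 vs 41.6 | 1/√0.80 = 1.118 | 73.2% |
| 30% | 72.8 vs 36.4 | 1/√0.70 = 1.195 | 69.0% |

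Under these assumptions the losses are upper bounds. The formula treats each visit alone, whereas the repeated-measures model recovers some information from a patient's other visits.

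**The case against.** The windows follow the protocol's schedule, which puts no tolerance on Days 3, 5, 7 and 10 and ±2 days on Days 14 and 28. They also have a stated purpose: SAP 6.4.3.4 and Appendix 2 want Day X to mean the same day for symptoms and viral load. Collection is supervised by a healthcare professional, and nothing in the documents shows that off-day sampling is common. All of this stands. It limits the likely size but does not remove the gap. A schedule without tolerance tells sites when to sample; it does not require a valid sample to go unused. No analysis planned in the SAP pairs symptoms with viral load by day, and the two models share only Days 5, 10 and 28.

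Three stronger readings are tempting, and the documents do not support them.

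- A reader might infer that the SAP admits sampling times are unreliable. It says that visit identifiers may be. Relabelling by date addresses wrong labels and is not evidence of off-day collection.
- A reader might infer that the analysis deciding proof of concept is damaged. The SAP gives more weight to viral-load analyses in the plural and names no single deciding one. The primary endpoint is still symptom resolution.
- A reader might infer that all viral-load results lose these samples. Time to clearance does not, Day 7 is not modelled, and the AUC text is silent.

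Nor does the SAP say outright that off-window samples are discarded. That follows from applying its classification with no reassignment rule.

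Simply adding ±1 day would not be enough. The windows would overlap at differences 3 and 5, and the SAP has no rule for one sample that fits two windows.

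**Conclusion.** The point holds in limited form and should be fixed. Applied literally, Appendix 2 leaves a viral-load sample one day off target out of the tables and, for Days 3, 5 and 10, out of the key secondary change-from-baseline model. The size cannot be derived from the documents. For off-day rates of 5% to 30%, the standard error at the affected visit grows by at most about 2.6% to 19.5%, assuming random loss that is equal across arms. Those figures concern precision only. Whether off-day collection is related to illness or differs by arm is unknown, so no claim of bias is made. The effect on the AUC depends on a detail that SAP 6.4.2.2 leaves open.

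**What to change.** For viral load only, replace the one-day windows with a table that covers every difference from 1 to 10:

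- 1–2 = Day 3, 4 = Day 5, 6–7 = Day 7, 8–10 = Day 10. Each is the nearest scheduled visit. Difference 1 is equally close to Day 1, but Day 1 is the pre-dose baseline, so the sample goes to Day 3.
- A sample midway between two visits (difference 3 or 5) goes to whichever adjacent visit has no sample of its own, with a fixed tie-break stated before unblinding. An early Day 5 or Day 7 sample is then kept when the preceding visit was on time.
- If several samples fall in one window, take the one closest to the target day instead of the first.
- Compute the AUC from actual sampling dates, and say so in SAP 6.4.2.2.
- Keep the exact-day classification as a sensitivity analysis.

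The cost is one lookup table, a few sentences of SAP text and one extra run of the model. The downside is about a day of timing blur within a visit, which is not negligible where visits are two days apart. Viral-load days would also no longer match symptom-score days exactly. The sensitivity analysis covers both.
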